9.6 Inclusion of Women and Minorities

The study is open to all participants regardless of gender or ethnicity. Review of accrual to past studies of new agents demonstrates the accrual of both genders and all NIH-identified ethnicities to such studies. The small number of patients entered into this trial will obviate any analysis of variation in response rate with gender or ethnicity.

10.0 RESPONSE CRITERIA

10.1 Bone Marrow Status Definitions

M1 Marrow

Less than 5% blasts in a bone marrow aspirate and at least 200 cells counted.

M2 Marrow

5-25% blasts in a bone marrow aspirate with at least 200 cells counted.

M3 Marrow

Greater than 25% blasts in a bone marrow aspirate with at least 200 cells counted.

10.2 Bone Marrow Response Criteria

10.2.1 Complete Remission (CR)

Attainment of M1 bone marrow with no evidence of circulating blasts or extramedullary disease and with recovery of peripheral counts (ANC \geq 500/ μ L and PLT count \geq 50,000 μ L). Qualifying marrow and peripheral counts should be performed within 1 week of each other.

10.2.2 Complete Remission with Incomplete Blood Count Recovery (CRi)

Attainment of M1 bone marrow with no evidence of circulating blasts or extramedullary disease, but with insufficient recovery of absolute neutrophil count (ANC < 500/ μ L) or platelets (< 50,000/ μ L).

10.2.3 Partial Remission (PR)

Complete disappearance of circulating blasts and achievement of M2 marrow status, without new sites of extramedullary disease, and with recovery of absolute neutrophil count (ANC \geq 500/ μ L).

10.2.4 Stable Disease (SD)

Patient does not satisfy the criterion for PD, and fails to qualify for CR, CRi, or PR.

10.2.5 Progressive Disease (PD)

An increase of at least 25% in the absolute number of circulating leukemic cells, development of new sites of extramedullary disease, or other laboratory or clinical evidence of PD, with or without recovery of ANC or platelets.

10.2.6 Toxic Death (TD)

Any patient who dies after receiving therapy on this protocol prior to receiving subsequent therapy.

10.2.7 Not evaluable (NE)

Patient does not satisfy the criterion for PD or ID, and either did not have a marrow evaluation, had inadequate marrow cell count, or had insufficient recovery of ANC to be classified as CR, CRp, PR, or SD.

10.3 CNS Status Definitions

CNS 1: In cerebral spinal fluid (CSF), absence of blasts on cytopsin preparation, regardless of the number of white blood cells (WBCs).

CNS 2: In CSF, presence < 5/μL WBCs and cytopsin positive for blasts, or ≥ 5 /μL WBCs but negative by Steinherz/Bleyer algorithm:

CNS 2a: < 10/μL RBCs; < 5/μL WBCs and cytopsin positive for blasts;

CNS 2b: ≥ 10/μL RBCs; < 5/μL WBCs and cytopsin positive for blasts; and CNS

2c: ≥ 10/μL RBCs; ≥ 5/μL WBCs and cytopsin positive for blasts but negative by Steinherz/Bleyer algorithm (see below)

CNS 3: In CSF, presence of ≥ 5/μL WBCs and cytopsin positive for blasts **and/or** clinical signs of CNS leukemia:

CNS 3a: < 10/μL RBCs; ≥ 5/μL WBCs and cytopsin positive for blasts;

CNS 3b: ≥ 10/μL RBCs, ≥ 5/μL WBCs and positive by Steinherz/Bleyer algorithm

CNS 3c: Clinical signs of CNS leukemia (such as facial nerve palsy, brain/eye involvement or hypothalamic syndrome)

METHOD OF EVALUATING INITIAL TRAUMATIC LUMBAR PUNCTURES:

If the patient has leukemic cells in the peripheral blood and the lumbar puncture is traumatic and contains ≥ 5 WBC/μL and blasts, the following Steinherz/Bleyer algorithm should be used

$$\frac{\text{CSF WBC}}{\text{CSF RBC}} > 2X \frac{\text{Blood WBC}}{\text{Blood RBC}}$$

A patient with CSF WBC ≥ 5/μL blasts, whose CSF WBC/RBC is 2X greater than the blood WBC/RBC ratio, has CNS disease at diagnosis.

Example: CSF WBC = 60/ μ L; CSF RBC = 1500/ μ L; blood WBC =46000/ μ L; blood RBC = 3.0 X 10⁶/ μ L:

CSF calculation	Blood calculation
$\frac{60}{1500} = 0.04$	$\frac{46000}{3.0 \times 10^6} = 0.015 \times 2 = .03$

Therefore this patient has CNS disease because 0.04 > 0.03

10.4 CNS Response Criteria

Only subjects with CNS 1 or 2 status will be enrolled. Those with active CNS disease (CNS 3) are excluded until they achieve CNS 1 or 2 status. CNS status will only be evaluated for progressive disease, defined as below.

10.4.1 Progressive Disease (PD): Any subject who develops CNS 3 disease will be considered to have progressive disease.

11.0 ADVERSE EVENT REPORTING REQUIREMENTS

11.1 Definitions

Adverse Event: An adverse event means any untoward medical occurrence associated with the use of a drug in humans, whether or not considered drug related.

Suspected Adverse Reaction: Any adverse event for which there is a reasonable possibility that the drug caused the adverse event. Reasonable possibility means there is evidence to suggest a causal relationship between the drug and the adverse event.

Unexpected Adverse Event or Unexpected Suspected Adverse Reaction: An adverse event or suspected adverse reaction is considered “unexpected” if it is not listed in the investigator brochure or is not listed at the specificity or severity that has been observed; or, if an investigator brochure is not available, is not consistent with the risk information described in the general investigational plan.

Serious Adverse Events or Serious Suspected Adverse Reactions: An adverse event or suspected adverse reaction is considered serious if, in the view of either the investigator or sponsor, it results in any of the following outcomes:

Death of Patient	An event that results in the death of a patient.
-------------------------	--

Life-Threatening	An event that, in the opinion of the investigator, would have resulted in immediate fatality if medical intervention had not been taken. This does not include an event that would have been fatal if it had occurred in a more severe form.
Hospitalization	An event that results in an admission to the hospital for any length of time. This does not include an emergency room visit or admission to an outpatient facility.
Prolongation of Hospitalization	An event that occurs while the study patient is hospitalized and prolongs the patient's hospital stay.
Congenital Anomaly	An anomaly detected at or after birth, or any anomaly that results in fetal loss.
Persistent or Significant Disability/Incapacity	An event that results in a condition that substantially interferes with the activities of daily living of a study patient. Disability is not intended to include experiences of relatively minor medical significance such as headache, nausea, vomiting, diarrhea, influenza, or accidental trauma (e.g., sprained ankle).
Important Medical Event Requiring Medical or Surgical Intervention to Prevent Serious Outcome	An important medical event that may not be immediately life-threatening or result in death or hospitalization, but based on medical judgment may jeopardize the patient and may require medical or surgical intervention to prevent any of the outcomes listed above (i.e., death of patient, life-threatening, hospitalization, prolongation of hospitalization, congenital anomaly, or persistent or significant disability/incapacity). Examples of such events include allergic bronchospasm requiring intensive treatment in an emergency room or at home, blood dyscrasias or convulsions that do not result in inpatient hospitalization, pregnancy, or the development of drug dependency or drug abuse.

Grade 3 fever and neutropenia is not an SAE unless a new hospitalization is required or is associated with another medical complication deemed medically important or life threatening.

11.2 Data Collection

Adverse events and suspected adverse reactions will be collected and reported on the electronic CRFs beginning with the first dose of study therapy until 30 days following the last dose of study therapy (or until the patient begins another therapy). The investigator will evaluate all adverse events and suspected adverse reactions as to their severity and relationship to Marqibo® as well as the regimen as a whole. Serious adverse events and suspected adverse reactions will require expedited reporting to the TACL Operations Center as described below.

11.3 Reporting Serious Adverse Events or Serious Suspected Adverse Reactions

11.3.1 The following serious adverse events or serious suspected adverse reactions requires expedited reporting:

- All Grade 5 events regardless of causality.
- All Grade 4 events that are possibly, probably or definitely related to Marqibo® or the regimen as a whole. Exclude reporting of hematologic toxicity as a serious adverse event unless the event meets the criteria of hematologic dose limiting toxicity per protocol section 4.2.1.2: The absence of peripheral blood count recovery (ANC > 500/ μ L and platelet count > 20,000/ μ L) 7 weeks (49 days) after the start of chemotherapy in the absence of persistent leukemia or documented myelosuppressive infection.
- All unexpected Grade 3 events that are possibly, probably or definitely related to Marqibo® or the regimen as a whole.

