Asparaginase Erwinia chrysanthemi (Erwinaze®), crisantapase (Erwinase®) asparaginase Erwinia chrysanthemi (recombinant)-rywn (Rylaze®) may be substituted for allergy to Pegaspargase. See below.

Drug Administration Details:

As per Cohort A, without mitoxantrone

Marqibo®

- Dose Level 1: 1.5 mg/m²/dose (no dose cap) given IV over 60 minutes (±10 minutes) on days 1, 8, 15 and 22.
- Dose Level 2: 2 mg/m²/dose (no dose cap) given IV over 60 minutes (±10 minutes) on days 1, 8, 15 and 22.
- Review list of concomitant medications that are prohibited (CYP3A4 inhibitors) or to be used with caution (Appendix 3). See section 4.5 for drug interactions.
- Dose will be given over 60 minutes ± 10 minutes

Other agents and instructions as detailed above in Cohort A, without mitoxantrone.

Cohort C: Modified Maintenance with Marqibo®

	Day 1	Day 2	Day 3	Day 4	Day 5	Day 8	Daily through day 13	Day 14
Marqibo®	●							Response Evaluator
Dexamathasone	●	●	●	●	●			
Methotrexate (PO)	●					●		
Mercaptopurine (PO)	●	●	●	●	●	●	●	
IT Methotrexate as needed no more than once weekly								

Marqibo®

- Dose Level 1: 1.5 mg/m²/dose (no dose cap) given IV over 60 minutes (±10 minutes) on day 1.
- Dose Level 2: 2 mg/m²/dose (no dose cap) given IV over 60 minutes (±10 minutes) on day 1.
- Review list of concomitant medications that are prohibited (CYP3A4 inhibitors) or to be used with caution (Appendix 3). See section 4.5 for drug interactions.
- Dose will be given over 60 minutes ± 10 minutes

Dexamethasone

- 6 mg/m²/day divided BID given orally on days 1 through 5. The two doses should be separated by at least 8 hours

- Any formulation of dexamethasone is acceptable

Methotrexate

- 20 mg/m²/dose given orally on day 1 and day 8.

Mercaptopurine

- 75 mg/m²/dose/day given orally, daily from days 1-13.

Intrathecal methotrexate

- Given intrathecally as needed, but no more than once weekly. Age-based dosing as below. Alternatively, per standard of care, ARA-C and hydrocortisone may be substituted if methotrexate is contraindicated.
- Timing of IT methotrexate is flexible in regard to timing of Marqibo®. However, these agents should not be given simultaneously in order to reduce the risk of administration route error.

Age (years)	Methotrexate (mg)
1-1.99	8 mg
2-2.99	10 mg
3-8.99	12 mg
≥ 9	15 mg

See appendix 8 for starting dose guidelines.

Dose modifications: (for patients without pre-existing disease related cytopenia)

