4.2 Dose Limiting Toxicity

Toxicity will be graded using the CTCAE criteria, version 4.03. The CTCAE provides descriptive terminology and a grading scale for each adverse event listed. A copy of the CTCAE can be downloaded from the CTEP home page (<http://ctep.cancer.gov>). Any dose-limiting toxicity (DLT) should be reported immediately through the TACL Operations Center to the Study Chair or Vice Chair. In addition to CTCAE, grading of sensory and motor neuropathies will be augmented by definitions listed in Appendix 5.

4.2.1 Definition of DLT: Dose limiting toxicity (DLT) will be defined as the occurrence of non-hematologic DLT and/or hematologic DLT as defined below.

4.2.1.1 Non-hematological DLT:

(Cohorts A and B) Any Grade 3 or greater non-hematological toxicity that is possibly, probably or definitely attributable to the protocol regimen and prevents a patient from receiving the required number of doses of therapy (as specified in Section 9.0) or from proceeding with further therapy by day 49 of the treatment cycle.

(Cohort C) Any Grade 3 or greater non-hematological toxicity that is possibly, probably or definitely attributable to the protocol regimen and prevents a patient from receiving the required number of doses of therapy (as specified in Section 9.0) or from proceeding with further therapy by day 21 of the treatment cycle for Stratum C.

4.2.1.2 Hematological DLT:

(Cohorts A and B) The absence of peripheral blood count recovery (ANC >500/ μ L and platelet count > 20,000/ μ L) 7 weeks (49 days) after the start of chemotherapy in the absence of persistent leukemia or documented myelosuppressive infection. Subjects with abnormal blood counts (Grade 1 through 4) at baseline due to disease will not be evaluable for hematologic DLT and will be considered not having had hematologic DLT for the purposes of the definition in 4.2.1.

(Cohort C) The absence of peripheral blood count recovery (ANC > 500/ μ L and platelet count > 20,000/ μ L) 3 weeks (21 days) after the start of chemotherapy in the absence of persistent leukemia or documented myelosuppressive infection. Subjects with abnormal blood counts (Grade 1 through 4) at baseline due to disease will not be evaluable for hematologic DLT and will be considered not having had hematologic DLT for the purposes of the definition in 4.2.1.

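### Section 11.3.1 contradicts its own cross-reference: it cites the hematologic DLT of section 4.2.1.2 but restates only the 49-day criterion of Cohorts A and B, not the 21-day criterion of Cohort C

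*Combined protocol and SAP*

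**What the plan says.** Section 11.3.1 lists the events that need expedited reporting. In the item on related Grade 4 events it tells sites not to report hematologic toxicity as an SAE "unless the event meets the criteria of hematologic dose limiting toxicity per protocol section 4.2.1.2". After a colon it writes that criterion out as no recovery of neutrophils and platelets "7 weeks (49 days) after the start of chemotherapy in the absence of persistent leukemia or documented myelosuppressive infection". No cohort is named.

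Section 4.2.1.2 contains two hematologic DLT criteria with the same count thresholds and different days:

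- Cohorts A and B: "7 weeks (49 days) after the start of chemotherapy".
- Cohort C: "3 weeks (21 days) after the start of chemotherapy in the absence of persistent leukemia or documented myelosuppressive infection".

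Three other provisions bear on the point:

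- Section 4.2 asks that any DLT be reported at once, through the TACL Operations Center, to the Study Chair or Vice Chair.
- Section 11.2 collects adverse events on the eCRF from the first dose "until 30 days following the last dose of study therapy", or until another therapy begins.
- Section 7.5 continues to collect treatment-related adverse events in follow-up and asks for prompt reporting of related toxicity.

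**The concern.** The colon presents the 49-day wording as the content of section 4.2.1.2. Take a site with a Cohort C patient whose counts have not recovered at day 21. In section 11.3.1 it finds an instruction to leave hematologic toxicity out and one written exception, which this patient does not meet. If it follows the cross-reference, it finds a criterion that the patient does meet. The two halves of one sentence give opposite answers.

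What depends on the answer is the SAE pathway: notice within 24 hours, the SAE Notification Form within 72 hours, and MedWatch reporting to the FDA (section 11.3.2), then IRB reporting (section 11.4). Under section 9.1.1 a DLT makes the patient not successfully treated. The same event could therefore count against the regimen in the primary endpoint while the SAE text tells the site not to report it.

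Myelosuppression is foreseeable in Cohort C. Its regimen includes daily mercaptopurine and oral methotrexate, and section 4.1 has count-based rules for holding mercaptopurine.

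**Working it through.** **Step 1. Reproduce the stated days.** 7 weeks × 7 = 49 days, which matches section 4.2.1.2 for Cohorts A and B. 3 weeks × 7 = 21 days, which matches section 4.2.1.2 for Cohort C. Only the first appears in section 11.3.1. The difference is 49 − 21 = 28 days.

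**Step 2. Check the 49-day text against the section 11.2 window.** I take 49 and 21 days as study days 49 and 21, as section 4.2.1.1 does for the non-hematologic DLT. The window ends on the day of the last dose + 30, or sooner if another therapy starts.

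- *Cohort C, one cycle.* The last scheduled drug is mercaptopurine, "75 mg/m²/dose/day given orally, daily from days 1-13". 13 + 30 = day 43, and 49 − 43 = 6 days short. If oral methotrexate on day 8 were the last dose, 8 + 30 = day 38. If Marqibo on day 1 were the last dose, 1 + 30 = day 31.
- *Cohort C, one cycle, with as-needed intrathecal methotrexate.* Section 4.1 sets no last day for it. Given at a restaging lumbar puncture on day 14 to 16, it moves the end to day 44 to 46. The window reaches day 49 only if some dose falls on day 49 − 30 = 19 or later.
- *Cohort C, two cycles.* Cycle 2 starts on day 15 to 22, so its day 13 is overall day 27 to 34. Adding 30 gives day 57 to 64, past day 49.
- *Cohorts A and B, on schedule.* The last Marqibo dose is on day 22, and 22 + 30 = day 52, past day 49. If the last dose given is dexamethasone on day 19, the window ends exactly on day 49.

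**Step 3. Check the Cohort C criterion against the same window.** In the single-cycle case, day 21 lies 43 − 21 = 22 days inside the window. The criterion in section 4.2.1.2 fits the Cohort C schedule; the one restated in section 11.3.1 does not.

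**Step 4. Check whether another route supplies the SAE report.** The section 4.2 notice passes through the Operations Center, which also files MedWatch reports and reports SAEs to the IRB. No text says that a DLT notice starts those steps; they follow from an event being reportable under section 11.3. Section 7.5 governs follow-up data and does not alter which hematologic events section 11.3.1 treats as reportable.

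**The case against.** A reader might infer that Cohort C hematologic DLTs are plainly excluded from expedited reporting. The documents do not support that. Section 11.3.1 cites section 4.2.1.2 by number, and that section contains the 21-day criterion. A site that follows the reference would report. The text contradicts itself; it is not a clear exclusion.

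A reader might also infer that adverse event collection stops on day 43, so that the 49-day criterion could never be met in single-cycle patients. That goes too far as well. Day 43 is the end of the section 11.2 window only, for Cohort C patients with one cycle and no later intrathecal dose. Section 7.5 keeps collecting related events. It also requires safety assessments at least every 30 days, until toxicities resolve or stabilize, in patients who discontinue for a possibly or probably related event. Cohorts A and B also receive a single course, and on schedule their window reaches day 52.

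Other points limit the consequence:

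- The Operations Center learns of every DLT at once under section 4.2, and section 9.2 monitors unsuccessful treatment in real time.
- Fatal events are reported in any case, because section 11.3.1 lists all Grade 5 events.
- Section 4.2.1.2 removes patients with disease-related abnormal baseline counts, persistent leukemia or a myelosuppressive infection, so few patients may be affected.
- Cohort C is at dose level 2 while Cohorts A and B are at level 1, but it receives one Marqibo dose per cycle against four, and section 9.2 expected it to be less toxic than Cohort A. The dose level alone is not an argument for greater risk.

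All of this stands and narrows the point. None of it removes the mismatch between sections 11.3.1 and 4.2.1.2.

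**Conclusion.** The point holds as a drafting inconsistency in an operative safety-reporting rule. Section 11.3.1 refers to a definition with two cohort-specific criteria and restates one. For a Cohort C patient the reference and the restatement disagree by 28 days on when failure of count recovery becomes reportable. On the literal restatement, a 21-day hematologic DLT would not be reported as an SAE.

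The six-day gap between day 43 and day 49 is supporting evidence that the 49-day wording does not fit the Cohort C schedule. It assumes one cycle, a last dose on day 13, no later intrathecal methotrexate, and the section 11.2 window alone. The documents give no expected rate of hematologic DLT in Cohort C, so the number of affected reports cannot be estimated. No sample size, decision rule or treatment rule depends on it. The correction is minor and worth making.

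**What to change.** Reconcile section 11.3.1 with section 4.2.1.2 in one of two ways:

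1. Delete the restated criterion and keep the cross-reference, adding that the hematologic DLT is the one defined for the patient's cohort. This leaves one definition in one place.
2. Restate both existing criteria, naming Cohorts A and B for the first and Cohort C for the second.

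Either option uses definitions already in the protocol and changes no treatment rule. The cost is a few words at the next amendment and possibly a few extra SAE reports.

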11.3.2 Steps for Reporting

Step 1: Identify the adverse event or suspected adverse reaction using the NCI Common Terminology Criteria for Adverse Events (CTCAE), version 4.03.

The CTCAE provides descriptive terminology and a grading scale for each adverse event listed. A copy of the CTCAE can be downloaded at <http://evs.nci.nih.gov/ftp1/CTCAE/About.html>.

Step 2: Grade the event using the NCI CTCAE version 4.03.

Step 3: Determine if the adverse event or suspected adverse reaction meets the criteria of being “serious”.

Step 4: Determine whether the adverse event or suspected adverse reaction is related to the protocol therapy.

The investigator will assess the causal relationship between the investigational product and the regimen as a whole and the adverse event. The investigator will use his/her clinical expertise and judgment to select the attribution category below that best fits the circumstances of the AE.

Attribution categories are as follows: Unrelated, Unlikely, Possible, Probable, and Definite.

Unrelated:

- The adverse event is *clearly unrelated* to the investigational agent(s).
- Does not follow a known response pattern to the suspect investigational product (if response pattern is previously known).
- Can be explained by the known characteristics of the patient’s clinical state or therapy administered to the patient.

Unlikely:

- The adverse event is *doubtfully* related to the investigational agent(s).
- May or may not follow a reasonable temporal sequence from administration of the investigational product.

- Likely explained by the known characteristics of the patient's clinical state or other therapy administered to the patient.

Possibly Related:

- The adverse event *may be* related to the investigational agent(s).
- Follows a reasonable temporal sequence from administration of the investigational product.
- May also be reasonably explained by the patient's clinical state or therapy administered to the patient.
- May follow a known response pattern to the investigational product (if response pattern is previously known)

Probably Related:

- The adverse event *is likely* related to the investigational agent(s).
- Follows a reasonable temporal sequence from administration of the investigational product.
- May follow a known response pattern to the investigational product (if response pattern is previously known)
- Could not be reasonably explained by the known characteristics of the patient's clinical state or other modes of therapy administered to the patient, if applicable;

Definitely Related:

- The adverse event is *clearly related* to the investigational agent(s).
- Follows the temporal sequence from administration of the investigational product
- Follows a known response pattern to the investigational product.
- Cannot be explained by the known characteristics of the patient's clinical state or other therapy administered to the patient.
- Is confirmed by improvement of symptoms on stopping or slowing administration of the investigational product and re-emergence of symptoms on restarting administration of the investigational product, (if applicable).

Step 5: Determine if the adverse event or suspected adverse reaction is "unexpected".

Step 6: Notify the TACL Operations Center by telephone or email

The following information should be submitted within 24 hours of event notification by either [contact] or Email [contact].

1. Patient TACL study ID and initials
2. Event description
3. Severity (CTCAE Grade)
4. Onset date
5. Reason event is considered serious

6. Dose of study drug and dates of administration
7. Investigator opinion of relationship to DRUG and the regimen as a whole
8. Name and phone number of physician in charge of the case
9. Name and phone number of CRA or Research nurse working with the case

Step 7: Submit a written report to the TACL Operations Center

Complete the TACL SAE Notification Form within 72 hours of learning of the event. The completed form can be emailed to [contact]. The form may also be faxed to [contact]. A follow-up SAE Notification Form must be submitted upon resolution of the event or interimly (prior to resolution) as requested by the study committee and/or TACL Operations Center. Please confirm via email or phone that the TACL Operations Center has received this notification. These serious adverse events will be reported to the FDA by the TACL Operations Office using the MedWatch form as required per federal regulations.

